9.5 Overdose

It is not expected that overdose with study drugs will occur. Total doses are contained within the study framework. The clinicians managing the study are clinical toxicologists.

9.6 Other Medications

Other than the study drugs and paracetamol, there are no additional prohibited medications. Rescue medication for nausea or vomiting is permitted. The protocol advocates the use of intravenous cyclizine in these circumstances. Any rescue medications should be recorded in the CRF.

Any medication (prescription as well as over the counter (OTC) drugs) or therapeutic intervention deemed necessary for the patient, and which, in the opinion of the Investigator, do not interfere with the safety and efficacy evaluations, may be continued. However, the Investigator should be cautious in evaluating the need for change in dosage and should carefully assess if any concomitant medication is necessary. If possible, all unnecessary concomitant medication should be stopped before entering the patient into this study. Concomitant medications received at least within 30 days prior to the patient providing written informed consent for the main study should be recorded.

9.7 Study Medication Accountability

The Investigator or designee is responsible for maintaining accountability records for all inventory transactions (i.e. receipt and return). Only personnel authorised by the PI should handle and administer the study medication. The study team must complete and return the study medication supply form to the Sponsor, verifying the receipt of study medication.

10 ADVERSE EVENTS AND SERIOUS ADVERSE EVENTS

10.1 Adverse Events

Participants will be instructed to alert the study team at any time after consenting to join the study, until discharge if any symptoms develop. All adverse events (AEs) identified must be recorded in detail in the CRF. If the patient has received a dose of study medication it should be deemed whether the AE is related or non-related to the study drug. Any AEs identified as part of the 7, 30 and 90 day follow up will be recorded/reported.

The Investigator is responsible for the detection and documentation of events meeting the criteria and definitions detailed below. In the case of an AE, the Investigator will initiate the appropriate treatment according to their medical judgment. Participants with AEs present at hospital discharge must be followed up until resolution of the event.

Page 34 of 46

Full details of contraindications and side effects that have been reported following administration of NAC can be found in the relevant Summary of Product Characteristics (SoPC) in Appendix B.

10.2 Definitions

An **adverse event** (AE) is any untoward medical occurrence in a clinical study patient who is administered a medicinal product, which does not necessarily have a causal relationship with the treatment.

An **adverse reaction** (AR) is any untoward or unintended response to an investigational medicinal product related to any dose administered.

An **unexpected adverse reaction** (UAR) is an adverse reaction that is not consistent with the product information in the IB/SoPC.

A serious adverse event (SAE), serious adverse reaction (SAR) or suspected unexpected serious adverse reaction (SUSAR) is any AE, AR or UAR that at any dose:

- results in death;
- is life threatening (i.e. the patient was at risk of death at the time of the event; it does not refer to an event which hypothetically might have caused death if it were more severe);
- requires hospitalisation or prolongation of existing hospitalisation;
- results in persistent or significant disability or incapacity;
- is a congenital anomaly or birth defect.

Note: Hospitalisations for treatment planned prior to randomisation and hospitalisation for elective treatment of a pre-existing condition will not be considered as an AE. Complications occurring during such hospitalisation will be AEs.

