Patients that do not require further NAC treatment will remain in the hospital for further 10hr and have a blood sample taken after 8hr. This blood sample will be after 20hr of starting NAC.

Follow-up:

There will be no follow-up visit, but patients will be followed up using their electronic records. The following data are collected 7, 30 and 90 days after randomisation: Representation to hospital (any reason), representation with liver injury, repeat overdose, death and transfer to liver transplantation unit. Any AEs or SAES identified will be recorded and reported.

Inclusion Criteria:

- 1. Any patient with capacity admitted to hospital within 24 hrs either a single acute POD or more than one dose of paracetamol (staggered) and deemed to require treatment with NAC.
- 2. Provision of written informed consent
- 3. Males and females of at least 16 years of age

These patients will include:

a) Patients presenting within 8h of overdose who have a timed blood paracetamol concentration above the 100-line on the UK APAP overdose treatment nomogram (See Figure 1).

b) Patients presenting later than 8h who are at risk of liver injury from the reported dose ingested and have blood results confirming need for NAC

c) Patients presenting after taking a staggered APAP overdose (defined as when the overdose of APAP is taken over a period of more than 1hr)

Exclusion Criteria:

- 1. Patients that do not have the capacity to consent to participate in the study
- 2. Patients detained under the Mental Health Act or deemed unfit by the Investigator to participate due to mental health.
- 3. Patients with known permanent cognitive impairment
- 4. Patients who are pregnant or nursing
- 5. Patients who have previously participated in the study
- 6. Unreliable history of POD
- 7. Patients presenting after 24hrs of POD
- 8. Patients who take anticoagulants (e.g. warfarin) therapeutically or have taken an overdose of anticoagulants
- 9. Patients who, in the opinion of the responsible clinician/nurse, are unlikely to complete the full course of NAC e.g. expressing wish to self-discharge
- 10. Prisoners
- 11. Non-English speaking patients. (Study information material will only be produced in English in view of the known and stable demographic of the Edinburgh self-harm population).

Study Procedures:

Independent Safety Data Monitoring Committee (SDMC):

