Calmangafodipir (PledOx[®]) had a safety profile in this study as would be predicted by non-clinical data. The most common preferred terms for safety reporting in the study (more than 25 events reported in total) were: neurotoxicity, thrombocytopenia, fatigue, nausea, neutropenia, peripheral sensory neuropathy, diarrhea, leukopenia, decreased appetite, anemia, paresthesia, neuropathy peripheral, vomiting and pyrexia. As expected, the frequencies of neurotoxicity, thrombocytopenia and neutropenia that were reported as AEs mirrored the reporting of these symptoms as chemotherapy-induced toxicities analyzed as efficacy data. Grade 2 neurotoxicity occurred in a smaller proportion of patients in the 5 μ mol/kg PledOx[®] group (4.4%, 2 events) compared to placebo (16.7%, 16 events). No other apparent differences between the treatment groups in terms of adverse events.

To date, approximately 150 patients with mCRC received repetitive dosing with calmangafodipir (PledOx[®]). Approximately 240,000 patients have received single doses of the closely related compound mangafodipir at similar or higher doses. No new significant safety data have emerged during the treatment reporting period. Immediate blood pressure fall, severe diarrhoea and severe vomiting, have previously been identified as important potential risks, to be closely monitored as the clinical program progresses.

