10.4.1 Assessment of Seriousness

The Investigator should make an assessment of seriousness as defined in Section 10.2.

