10.4.3 Assessment of Severity

The Investigator should make an assessment of severity for each AE/SAE and record this on the CRF according to one of the following categories:

Mild: an event that is easily tolerated by the participant, causing minimal discomfort and not interfering with every day activities.

Moderate: an event that is sufficiently discomforting to interfere with normal everyday activities.

Severe: an event that prevents normal everyday activities.

Note: the term 'severe', used to describe the intensity, should not be confused with 'serious' which is a regulatory definition based on participant/event outcome or action criteria. For example, a headache may be severe but not serious, while a minor stroke is serious but may not be severe.

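### Section 10.2 has no seriousness criterion for medically important events, so a severe PP100-01 reaction treated on the ward need not be an SAE

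*Protocol*

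**What the plan says.** Protocol section 10.2 uses one list for SAE, SAR and SUSAR. An event qualifies if it causes death, "is life threatening (i.e. the patient was at risk of death at the time of the event"), "requires hospitalisation or prolongation of existing hospitalisation", causes lasting or significant disability, or "is a congenital anomaly or birth defect". The list ends there. The life-threatening item expressly leaves out an event that would have been fatal only had it been worse.

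No other section widens the list. Section 10.4.1 says: "The Investigator should make an assessment of seriousness as defined in Section 10.2". Section 10.4.3 separates intensity from seriousness: severe "should not be confused with 'serious' which is a regulatory definition based on participant/event outcome or action criteria". Section 7.1.9 treats vomiting as an SAE only where it has been classified as serious.

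On timing, section 7.1.7 puts the bolus at 2 h after NAC starts. The synopsis (end of treatment) adds: "Patients that do not require further NAC treatment will remain in the hospital for further 10hr". The lay summary gives a total of 22 h.

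On expected toxicity, section 2.3 says: "Immediate blood pressure fall, severe diarrhoea and severe vomiting, have previously been identified as important potential risks".

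**The concern.** In an outpatient trial, the hospitalisation criterion picks up many acute reactions that are bad enough to need treatment. Here every patient is already in hospital when the bolus is given and is due to stay for most of a day afterwards. The criterion is left with only its second limb, prolongation, and there is no medically-important item to fill the space.

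Four things in the plan depend on the word *serious*:

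- the report to the safety vendor within 24 h (sections 10.5 and 10.6);
- the SAR and SUSAR listing in the annual safety report (section 10.6);
- the SAE proportions and their confidence intervals, which are part of the primary analysis (SAP 4.4);
- the second pause rule, which needs one SUSAR judged probably or definitely related (section 10.10).

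A reaction can be severe, treated and attributed to PP100-01 and still reach none of them. This matters because section 13.1 describes the risks of the combination as unknown, and the named drug risks are acute ones.

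**Working it through.** **Step 1. The inpatient window.** Inputs: loading infusion 2 h and second infusion 10 h (section 9.1); further stay 10 h (synopsis).

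- Planned stay = 2 + 10 + 10 = 22 h, which reproduces the protocol's own figure.
- Planned inpatient time after the bolus = 22 − 2 = 20 h.

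Patients who need more NAC stay longer, so 20 h is the shortest planned window.

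**Step 2. Test each criterion on one type of event.** Take a severe reaction that begins after the bolus, is treated on the ward and settles within the 20 h.

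| Criterion in 10.2 | Can it apply? |
|---|---|
| Death | No, by description |
| Life threatening | Only if the patient was actually at risk of death |
| New hospitalisation | No, already an inpatient |
| Prolonged hospitalisation | Only if discharge is delayed |
| Disability or incapacity | Normally not, as the event has settled |
| Birth defect | Not applicable |

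Two routes to SAE status remain: actual risk of death, and a longer stay. An event that takes neither is not serious under 10.2, whatever its intensity grade.

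**Step 3. Follow the consequences.** Without SAE status, section 10.5 imposes no 24 h report. The event cannot be a SAR or SUSAR, so the SUSAR pause rule cannot fire. The other pause rule needs a death, or admission to critical care or a liver transplantation unit. Scheduled committee review comes when a cohort is complete (synopsis). The 24 h gap after the first dosed patient in each cohort (section 6.6.1) states no event criterion. Dose-limiting toxicity is mentioned in sections 6.7 and 12.3 but never defined, so it gives no second threshold.

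**Step 4. How often the definition could matter.** The documents give no rate for this type of event, so the rate p is an assumption. With patients independent:

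P(at least one among n dosed patients) = 1 − (1 − p)^n

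| Assumed p | Cohort, n = 6 | All dosed, n = 18 |
|---|---|---|
| 5% | 1 − 0.95^6 = 0.265 | 1 − 0.95^18 = 0.603 |
| 10% | 1 − 0.90^6 = 0.469 | 1 − 0.90^18 = 0.850 |
| 20% | 1 − 0.80^6 = 0.738 | 1 − 0.80^18 = 0.982 |

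These are probabilities that an event of this type occurs. That such events add nothing to the SAE count follows from how they are described and is not a separate result.

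**The case against.** A reader might infer that any severe bolus reaction treated on the ward falls outside the SAE definition and goes unreported. The documents do not support that:

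- A reaction that puts the patient at risk of death or lengthens the stay is serious wherever it is treated, and an abrupt fall in blood pressure may well do the first.
- Prolongation is plausible. Section 9.3 manages anaphylactoid reactions by interrupting the infusion and restarting it more slowly. NAC then ends later, and the further 10 h stay follows it.
- Section 10.6 asks for contact within 24 h about a *potential* SAE. This may prompt some extra calls, although it does not add a criterion.

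A reader might also infer that the trial is blind to acute reactions. It is not:

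- AEs are half of the primary outcome, are sought at 2, 2.5, 10, 20 and 22 h (section 7.1.9), and are all recorded (section 10.1).
- SAP 4.4 tabulates them by intensity, treatment given, relationship and action taken. SAP 4.6 analyses anaphylactoid reactions separately, and SAP 4.9 lists every event.
- The committee reviews accumulating AE data and sees safety data before each dose step. Critical care admission pauses enrolment without any SAE label.

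Two further limits are fair. A SUSAR must also be unexpected against the Investigator's Brochure or product summary, which are not available here; reactions the sponsor already names may be listed there. And sections 15.1 and 15.2 cite GCP and the UK regulations without their text, so the documents cannot show that a sixth criterion is required.

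These points shrink the concern without removing it. None of them gives SAE status, or a clear 24 h duty, to a severe reaction that neither threatens life nor delays discharge.

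**Conclusion.** The point holds in a limited form and is a cheap improvement. The five-item list, together with 20 h of planned inpatient time after the bolus, leaves a class of severe, treated reactions that need not be SAEs. What is missing for them is expedited reporting, a place in the SAE proportions, and any route to the SUSAR pause. Detection, AE tabulation and committee review between cohorts are intact.

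The size depends on a rate the documents do not give. Across assumed rates of 5% to 20%, the chance of at least one such event is 26% to 74% per cohort of six and 60% to 98% across the 18 dosed patients. The conclusion about classification does not depend on those rates; it rests on the wording of 10.2 and the 22 h timeline alone.

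**What to change.** Add a sixth criterion to section 10.2 and to the SAE form: *is an important medical event that, in the investigator's judgement, jeopardised the patient or needed intervention to prevent one of the outcomes above*. Sections 10.5, 10.6 and 10.10 and the SAE tables in SAP 4.4 then work without further edits. No dose, treatment or pause rule changes.

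The cost is one line, a short briefing for site staff, and a few more SAE reports among 24 patients. Two limits remain. The criterion relies on judgement, so some treated reactions that settle will still be classed as non-serious. SUSAR status will still require the reaction to be unexpected.

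The same definition should apply to all three cohorts. If patients have already been dosed, their recorded AEs should be reclassified under it, because otherwise SAE proportions would not be comparable between dose groups.

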10.3 Detecting AEs and SAEs

All AEs and SAEs must be recorded from the time a participant consents to join the study until hospital discharge.

The Investigator should ask about the occurrence of AEs/SAEs during the infusion and until hospital discharge. Open-ended and non-leading verbal questioning of the participant should be used to enquire about AE/SAE occurrence. If there is any doubt as to whether a clinical observation is an AE, the event should be recorded.

Patient electronic records will be reviewed at 7 days, 30 and 90 days after discharge for AEs and SAEs.

10.4 Recording AEs and SAEs

When an AE/SAE occurs, it is the responsibility of the Investigator to review all documentation (e.g. hospital notes, laboratory and diagnostic reports) related to the event. The Investigator should then record all relevant information in the AE log and on the SAE form (if the AE meets the criteria of serious).

Information to be collected includes dose, type of event, onset date, Investigator assessment of severity and causality, date of resolution as well as treatment required, investigations needed and outcome.

10.4.1 Assessment of Seriousness

The Investigator should make an assessment of seriousness as defined in Section 10.2.

10.4.2 Assessment of Causality

The Investigator must make an assessment of whether the AE/SAE is likely to be related to treatment according to the following definitions. All AEs/SAEs judged as having a reasonable suspected causal relationship (e.g. possibly, probably, definitely) to the study drug will be considered as ARs/SARs. If concomitant or rescue/escape drugs are given, the Investigator must also make an assessment of whether the AE/SAE is likely to be related to an interaction between the study drug and concomitant or rescue/escape drugs or whether the AE/SAE might be linked to either the study drug or concomitant or rescue/escape drugs but cannot be attributed to only one of these drugs. All AEs/SAEs judged as being related (e.g. possibly, probably, definitely) to an

interaction between the study drug and concomitant or rescue/escape drugs, or any AE/SAE that cannot be attributed to only the study drug or the concomitant or rescue/escape drugs will also be considered to be ARs/SARs.

Unrelated: where an event is not considered to be related to the study drug.

Possibly: although a relationship to the study drug cannot be completely ruled out, the nature of the event, the underlying disease, concomitant medication or temporal relationship make other explanations possible.

Probably: the temporal relationship and absence of a more likely explanation suggest the event could be related to the study drug.

Definitely: The known effects of the study drug or its therapeutic class, or based on challenge testing, suggest that study drug is the most likely cause.

Alternative causes such as natural history of the underlying disease, other risk factors and the temporal relationship of the event to the treatment should be considered and investigated. The blind should not be broken for the purpose of making this assessment.

10.4.3 Assessment of Severity

The Investigator should make an assessment of severity for each AE/SAE and record this on the CRF according to one of the following categories:

Mild: an event that is easily tolerated by the participant, causing minimal discomfort and not interfering with every day activities.

Moderate: an event that is sufficiently discomforting to interfere with normal everyday activities.

Severe: an event that prevents normal everyday activities.

Note: the term 'severe', used to describe the intensity, should not be confused with 'serious' which is a regulatory definition based on participant/event outcome or action criteria. For example, a headache may be severe but not serious, while a minor stroke is serious but may not be severe.

10.4.4 Assessment of Expectedness

If an event is judged to be an AR/SAR, the evaluation of expectedness should be made based on knowledge of the reaction and the relevant product information documented in the IB/SoPC.

10.5 Reporting of SAEs/SARs/SUSARs

Once the Investigator becomes aware that an SAE has occurred in a study participant, they must report the information to PRODUCTLIFE within 24 hrs. The SAE form must be completed as thoroughly as possible with all available details of the event, signed by the Investigator. If the Investigator does not have all information regarding an SAE, they should not wait for this additional information before notifying PRODUCTLIFE. The form can be updated when the additional information is received.

The SAE report must provide an assessment of causality and expectedness at the time of the initial report.

The SAE will be reported by PRODUCTLIFE Ltd, [name], United Kingdom, [contact], [contact], Web: www.productlife-group.com, E-mail: [contact].

10.6 Regulatory Reporting Requirements

As soon as the Investigator is aware of a potential Serious Adverse Event (SAE), he/she should contact PRODUCTLIFE by telephone ([contact]) or E-mail ([contact]) no later than 24 hours after the knowledge of such a case. Reporting of the SAE via E-mail must be done by E-mailing an SAE form to [contact].

If identification of the event occurs outside of office hours, the SAE form must be sent to [contact] or faxed ([name]) where the PRODUCTLIFE safety team will become aware of it at the start of the next business day (8.30 - 17.00). Urgent out-of-CONFIDENTIAL

hours calls will be redirected to and qualified safety team member who will record the details of the call. The SAE must contain the minimum criteria for the case to be valid: an identifiable patient, suspect treatment/drug, adverse event and a reporter. Information regarding the causality should also be provided. The Investigator should follow-up the initial notification of the potential SAE by E-mailing a copy of the SAE reporting form to PRODUCTLIFE at the number provided in the Investigator Site File. The E-mailed SAE reporting form should be received at PRODUCTLIFE within 24 hours after knowledge of such a case.

A Development Safety Update Report will be submitted to the regulatory competent authority and the main REC listing all SARs and SUSARs.

10.7 Follow up Procedures

After initially recording an AE or recording and reporting an SAE, the Investigator is required to follow each participant until resolution. Follow up information on an SAE should be reported to PRODUCTLIFE.

Follow-up information on an existing SAE that is fatal or life-threatening should be reported by the Investigator to PRODUCTLIFE within 5 days after the initial report. Where appropriate, hospitalisation or autopsy reports should be made available. All serious adverse events will be followed up until resolution (i.e., asymptomatic, stabilisation or death).

AEs still present in participants at hospital discharge should be monitored until resolution of the event or until no longer medically indicated.

10.8 Reporting of Suspected Unexpected Serious Adverse Reactions by PRODUCTLIFE

Suspected unexpected serious adverse reactions (SUSARs) will be reported by PRODUCTLIFE according to appropriate Competent Authority and Ethics Committee requirements. Sponsor will report SUSARs to the Investigator in a blinded manner, following appropriate notification to the Competent Authorities and Ethics Committees. SUSAR reporting to the Competent Authorities and Ethics Committees will be performed according to local regulations in an unblinded manner. The Competent Authorities will be notified of all SUSARs through the Eudravigilance database.

Fatal and life-threatening SUSARs should be reported by PRODUCTLIFE as soon as possible to the Competent Authorities and Ethics Committees according to local regulations, and in any case no later than 7 calendar days after knowledge by PRODUCTLIFE of such a case. Relevant follow-up information on the case will be subsequently communicated within an additional 8 days. All other SUSARs shall be reported to the Competent Authorities concerned and to the Ethics Committee concerned according to local regulations as soon as possible but within a maximum of 15 days of first knowledge by PRODUCTLIFE.

